2. STUDY OBJECTIVES

2.1.1 Primary objective

The primary objective of this study is to demonstrate safety and tolerability of durvalumab and tremelimumab and palliative radiation therapy in patients with recurrent metastatic squamous cell carcinomas of the head and neck previously exposed to an anti PD-1 or PDL-1 monoclonal antibody

2.1.2 Secondary objective(s)

- 2.1.2.1** Measure objective response rates based on RECIST 1.1. criteria in patients receiving the durvalumab, tremelimumab and palliative RT combination
- 2.1.2.1** Determine overall and progression free survival in patients enrolled in the study

2.1.3 Exploratory objective(s)

- 2.1.3.1** Collect serum and archived (or fresh) tissue for correlative studies.

[figure not shown]
3. STUDY DESIGN

3.1 Overview of study design

This study will be carried out as a single institution, single arm phase I/II unblinded trial. A maximum of 20 patients will be enrolled. Each patient will be treated with durvalumab, tremelimumab and palliative hypofractionated radiation therapy using either HIGRT or SBRT. Durvalumab will be continued for 13

cycles, unless evidence of unacceptable toxicity, disease progression or withdrawal of patient consent were to occur.

3.2 Study Schema

The first 6 patients of this study will represent the initial run-in phase of the triplet combination of durvalumab, tremelimumab and HIGRTor SBRT. Fixed doses of Durvalumab and Tremelimumab will be administered on day 1 of therapy. Radiation will be initiated on Week 3 of the 28 day cycle. Radiation will be delivered to a total dose of 24 Gy, given in 3 fractions of 8Gy every other day. Durvalumab will be continued for a total of 13 cycles, and tremelimumab for a total of 4 cycles unless patient withdraws consent, has confirmed disease progression, and/or develops toxicity that results in treatment discontinuation.

Serum correlative studies will be collected at the following timepoints: at baseline, prior to cycle #2, and prior to cycle#4 of treatment. Archived formalin fixed paraffin embedded tissue will be collected from patients enrolled. If the patient does not have archived tissue available, a fresh biopsy will be obtained.

3.3 Study Oversight for Safety Evaluation

The primary endpoint of this study is safety and tolerability. Durvalumab and tremelimumab will be given at the recommended fixed dosing in patients > 30kg (see section 1.3.1), which has been shown to result in minimal toxicity, but encouraging efficacy in NSCLC patients. Since the concurrent administration of radiation therapy is previously unstudied in this cohort, the first 6 patients will represent a run-in phase, and enrollment will be halted until all patients complete

the first two cycles of treatment (8weeks) These 6 patients will be assessed for DLTs and will determine if a modified dosing schedule of durvalumab and tremelimumab will be applied in the expansion phase.

In keeping with the study primary endpoint, a stopping rule will be implemented in the unlikely event that the combination under study is deemed to have unacceptably high toxicities. Enrollment will be halted if more than 3 patients experience a Grade 4 or higher drug related toxicity (CTCAE v. 4) during the trial or up to 30 days after the last investigational drug infusion. The likelihood of observing 3 or more Grade 4+ drug-related DLTs is 80% if the true rate is 20% and the likelihood is 91% if the true rate is 25%. This rule has an 83% chance of stopping in the 1st 10 patients if the true rate is 40%. Section 10.2.2 provides some guidelines on the attribution of toxicity to the drug and radiation combination. The study will be reviewed by the University of Washington/Fred Hutchinson Cancer Research Center Data Safety and monitoring board.

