11.2.4 Interim analyses

No interim analysis is planned for this study.

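### The enrolment stopping rule acts at the 4th patient with Grade 4+ toxicity, but its three supporting probabilities are those of a rule that acts at the 3rd

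*Combined protocol and SAP*

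**What the plan says.** Three consecutive statements in Section 3.3 of the protocol set and justify the rule.

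- The trigger: "Enrollment will be halted if more than 3 patients experience a Grade 4 or higher drug related toxicity (CTCAE v. 4"), counted "during the trial or up to 30 days after the last investigational drug infusion".
- The first justification: "The likelihood of observing 3 or more Grade 4+ drug-related DLTs is 80% if the true rate is 20" per cent, and "the likelihood is 91% if the true rate is 25" per cent.
- The second justification: "This rule has an 83% chance of stopping in the 1st 10 patients if the true rate is 40" per cent.

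On sample size, Section 3.1 says: "A maximum of 20 patients will be enrolled". Section 11.2.4 says: "No interim analysis is planned for this study". Sections 11.2.1 to 11.3 do not mention the stopping rule, and no other section restates or reconciles the threshold.

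**The concern.** More than 3 patients and 3 or more patients are different rules. The trigger uses one and the supporting probabilities use the other.

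Safety is the primary endpoint, and this is the only numerical stopping boundary that covers the whole trial. The run-in rule looks at the first 6 patients and changes the dosing schedule; it does not stop the study. If the trigger is applied as worded, those overseeing the trial have been given detection probabilities that the rule does not deliver. There is also a practical difficulty: when the third qualifying patient occurs, the trigger says to continue, whereas the quoted figures assume that enrolment has stopped.

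A second mismatch is in what is counted. The trigger counts drug-related toxicities of Grade 4 or higher over the whole trial. The justification counts DLTs, which Section 6.4 evaluates only in the first 6 patients over 28 days.

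**Working it through.** **Inputs.** From Section 3.3: true rates of 20%, 25% and 40%; stated probabilities of 80%, 91% and 83%; 10 patients for the last figure. From Section 3.1: a maximum of 20 patients, used for the first two figures.

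**Formula.** With X the number of patients with an event among n, each with probability p:

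P(X ≥ r) = 1 − Σ C(n,k) pᵏ (1−p)ⁿ⁻ᵏ, summed over k = 0 to r−1.

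**Step 1: reproduce the stated figures with r = 3.**

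- n = 20, p = 0.20: 1 − (0.0115 + 0.0576 + 0.1369) = 0.7939 (stated 80%)
- n = 20, p = 0.25: 1 − (0.0032 + 0.0211 + 0.0669) = 0.9087 (stated 91%)
- n = 10, p = 0.40: 1 − (0.0060 + 0.0403 + 0.1209) = 0.8327 (stated 83%)

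All three match to within one point.

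**Step 2: the rule as written, r = 4.** Subtract P(X = 3) from each result.

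- n = 20, p = 0.20: 0.7939 − 0.2054 = 0.5886 (from unrounded terms)
- n = 20, p = 0.25: 0.9087 − 0.1339 = 0.7748
- n = 10, p = 0.40: 0.8327 − 0.2150 = 0.6177

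| Setting | Stated | 3 or more | 4 or more (as written) | Stated minus as written |
|---|---|---|---|---|
| n = 20, rate 20% | 80% | 79.4% | 58.9% | 21.1 points |
| n = 20, rate 25% | 91% | 90.9% | 77.5% | 13.5 points |
| n = 10, rate 40% | 83% | 83.3% | 61.8% | 21.2 points |

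**Step 3: rule out other explanations.** Thresholds of 2 or 5 do not fit either. In the same three settings, 2 or more gives 93.1%, 97.6% and 95.4%, and 5 or more gives 37.0%, 58.5% and 36.7%. A different denominator does not rescue the written trigger. With 4 or more, about 26 to 27 patients would be needed for the 80% (79.3% at 26, 81.8% at 27), 26 for the 91% (92.0%) and 13 for the 83% (83.1%).

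**Step 4: consequences.** At a true 20% rate, the chance that the threshold is not reached in 20 patients is 1 − 0.589 = 41%, against the 20% implied by the stated figure. Expected enrolment up to a maximum of 20, with outcomes known at once, is the sum of P(fewer than r events in the first k patients) over k = 0 to 19:

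| True rate | 3 or more | 4 or more |
|---|---|---|
| 20% | 13.57 | 16.51 |
| 25% | 11.53 | 14.62 |
| 40% | 7.49 | 9.95 |

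**Step 5: the DLT wording.** Among the 6 run-in patients, 3 or more events at a 20% rate has probability 1 − (0.2621 + 0.3932 + 0.2458) = 9.9%. The 80% therefore cannot refer to DLTs as Section 6.4 defines their evaluation.

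**The case against.** Several points can fairly be made on the plan's side.

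- The 80% and 91% are openly labelled as probabilities of 3 or more and are right for that event. This stands. The error there is that they are offered in support of a rule with a different trigger. The 83% has no such label and is credited to the rule.
- The trigger wording may be the slip. If 3 or more was intended, all three figures stand and only one phrase is wrong. The documents do not settle this, but either way Section 3.3 contradicts itself.
- The values for 4 or more are not exact chances of halting. An event in patient 20, or after accrual closes, cannot halt enrolment. Stopping before patient 20 enters needs 4 events in the first 19 patients: 54.5% at a 20% rate and 73.7% at 25%. This is correct, and it makes 58.9% and 77.5% upper limits.
- Other safeguards exist: the pause after 6 patients (Section 3.3), the monitoring committee (Section 13.2.1), weekly review of adverse events (Section 14) and the power to end the study for safety (Section 13.3). They limit the consequence, but after the run-in none of them carries a numerical threshold that could supply the stated probabilities.
- The DLT wording is a matter of terminology, because the figures reproduce at n = 20. That is so, but it should be corrected in the same edit.

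**Conclusion.** The concern holds. The trigger and its operating characteristics disagree, and the rule as worded falls short of the quoted probabilities by 13.5 to 21.2 points. The 83% is wrong for the written rule, whose value is 61.8%. The 80% and 91% describe an event one patient short of the trigger.

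The calculation assumes independent patients, one common event rate and outcomes known immediately. The last assumption favours the plan: the counting window runs to 30 days after the last infusion, so late events would lower the chance of stopping within the first 10 enrolled under either threshold. The conclusion does not depend on which threshold was intended. It needs correction because it concerns the trial-wide safety boundary in a study whose primary endpoint is safety.

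**What to change.** Amend Section 3.3 so that one threshold is used throughout. There are two consistent versions, and the choice between them belongs to the sponsor with the monitoring board.

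- **Keep more than 3 patients.** Restate the probabilities for 4 or more: 59% (20 patients, true rate 20%), 77% (20 patients, 25%) and 62% (first 10 patients, 40%).
- **Set the trigger at 3 or more patients.** The stated figures then stand, with 79% in place of 80%.

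In either case, replace DLTs in the justification with drug-related toxicities of Grade 4 or higher. Say also that the figures are probabilities of observing that many events with outcomes known at once, and so upper limits on the chance of actually halting accrual.

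The edit is a sentence or two. Under the first version, the published figures become less favourable. Under the second, a halt at a low true rate becomes more likely: the probability of reaching the threshold in 20 patients rises from 1.6% to 7.5% at a true rate of 5%, and from 13.3% to 32.3% at 10%. Stating these values beside the others would let the board see both sides of the choice.

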1.1.5 Radiation therapy

Uncontrolled loco regional disease is a major concern in head and neck cancer as it severely compromises a patient's quality of life with pain, ulceration, bleeding, foul odor, speech, swallowing, and breathing difficulties etc. Historically, radiation therapy has underpinned any and all attempts at providing durable disease control in the head and neck region.

In this protocol, palliative radiation therapy will be administered using either hypofractionated Image guided Radiotherapy (HIGRT) or Stereotactic ablative body radiotherapy (SBRT). These two techniques involve precise delivery of large tumoricidal/ablative doses of radiation treatments to a small tumor over 1-5 fractions using image guidance and elaborate treatment planning process aimed at providing steep dose gradients especially near critical organs. Distinct nontraditional radiobiological mechanisms may be involved with the high dose fractions ($>/= 6$ Gy) used with HIGRT/SBRT, as compared with conventionally fractionated (1.8-2 Gy) radiotherapy that is commonly used in the curative setting. HIGRT/SBRT may produce biological effects mediated through enhanced immune stimulation and endothelial damage of the tumor micro environment. (Karam et al. Future Oncol. 2015). As a primary modality for medically unfit patients, SBRT has offered reasonable local control with acceptable toxicity. In the re-irradiation setting, SBRT is associated with higher rates of morbidity (10-50%) and even mortality (1-5%) in the face of promising local control.

There is now increasing data on the feasibility of hypofractionated radiation administered concurrent with immune checkpoint inhibition. Recent publication of the randomized phase 2 SABR-COMET study (Palma et al. Lancet 2019) (SBRT) in the oligometastatic setting significantly improves overall survival and progression free survival compared to palliative standard of care. This trial targeted all known metastatic lesions and was not in combination

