10.2.2 Assessment of relationship

An investigator who is a qualified provider will evaluate all adverse events according to the NCI Common Terminology for Adverse Events (CTCAE), version 4.03. Any adverse event which

changes CTCAE grade over the course of a given episode will have each change of grade recorded on the adverse event case report forms/worksheets.

All adverse events regardless of CTCAE grade must also be evaluated for seriousness.

The determination of the likelihood that durvalumab and/or tremelimumab caused the adverse event will be provided by an investigator who is a qualified physician. The investigator's signed/dated initials on the source document or worksheet that supports the causality noted on the AE form, ensures that a medically qualified assessment of causality was done. This initialed document must be retained for the required regulatory time frame. The criteria below are intended as reference guidelines to assist the investigator in assessing the likelihood of a relationship between the test drug and the adverse event based upon the available information.

The following components are to be used to assess the relationship between durvalumab and/or tremelimumab and the AE; the greater the correlation with the components and their respective elements (in number and/or intensity), the more likely that durvalumab and/or tremelimumab caused the adverse event (AE):

- Is there evidence that the subject was actually exposed to durvalumab and tremelimumab such as: reliable history, acceptable compliance assessment expected pharmacologic effect, or measurement of drug/metabolite in bodily specimen?
- Did the AE follow in a reasonable temporal sequence from administration of durvalumab and tremelimumab?
- Is the time of onset of the AE compatible with a drug-induced effect (applies to trials with investigational medicinal product)?
- Is the AE not reasonably explained by another etiology such as underlying disease, other drug(s)/vaccine(s), or other host or environmental factors

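### The stopping rule is aimed at toxicity of the drug and radiation combination, but as worded it does not count Grade 4+ events attributed to radiation alone

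*Combined protocol and SAP*

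**What the plan says.** Section 3.3 ties the stopping rule to the primary endpoint, safety and tolerability. It says the rule applies "in the unlikely event that the combination under study is deemed to have unacceptably high toxicities". Sections 3.1 and 3.2 define that combination as durvalumab, tremelimumab and hypofractionated radiation. Section 3.3 also identifies concurrent radiation as the element not previously studied in this cohort.

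The operative sentence is: "Enrollment will be halted if more than 3 patients experience a Grade 4 or higher drug related toxicity (CTCAE v. 4"). The counting period runs through the trial and up to 30 days after the last drug infusion.

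On attribution, Section 3.3 states: "Section 10.2.2 provides some guidelines on the attribution of toxicity to the drug and radiation combination". Section 10.2.2 opens its list of criteria with: "The following components are to be used to assess the relationship between durvalumab and/or tremelimumab and the AE". Radiation is not mentioned there.

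Section 10.3 asks for a yes/no causality rating against durvalumab or tremelimumab for every adverse event. A causality assessment for radiation appears only among the extra items collected for serious adverse events. Section 11.2.1 will report relationship to the experimental agents and does not say whether radiation is one of them.

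**The concern.** The aim of the rule and the event it counts do not match. A Grade 4 or 5 event that the investigator attributes solely to radiation is toxicity of the combination, but it is not drug-related and so adds nothing to the count. The section cited to settle attribution does not cover radiation.

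This matters because safety is the primary endpoint and this is the only numeric trigger that runs through the whole trial. Radiation-only events are foreseeable. Section 4.1 (criterion 6) admits previously irradiated sites, Section 5.3.3 makes separate provision for re-irradiation, and Section 1.1.5 reports 10-50% morbidity and 1-5% mortality for SBRT in that setting.

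**Working it through.** **Step 1. The passages side by side.**

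| Section | Role | Covers radiation? |
|---|---|---|
| 3.3, aim | What the rule protects against | Yes, the whole combination |
| 3.3, rule | Event counted | Drug-related Grade 4+ only |
| 3.3, cross-reference | Where attribution is explained | Says yes, pointing to 10.2.2 |
| 10.2.2 | Attribution criteria | No, the two drugs only |
| 10.3, all adverse events | Causality rating | No, the two drugs only |
| 10.3, serious adverse events | Extra causality item | Yes, with no criteria and no link to 3.3 |
| 11.2.1 | Reported relationship | Not stated |

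The last criterion in 10.2.2 begins "Is the AE not reasonably explained by another etiology such as underlying disease". An event that radiation explains therefore tends away from a drug-related rating.

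The outcome under the literal wording is:

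- attributed to drug: counts;
- attributed to drug and radiation: counts;
- attributed to radiation alone: does not count.

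**Step 2. The printed probabilities.** Section 3.3 states "The likelihood of observing 3 or more Grade 4+ drug-related DLTs is 80% if the true rate is 20" per cent, and gives 91% at a true rate of 25%. It adds "This rule has an 83% chance of stopping in the 1st 10 patients if the true rate is 40" per cent. Taking n = 20 (the maximum enrolment in Section 3.1) for the first two and n = 10 for the third, the chance of at least r patients with a counted event is

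P(X ≥ r) = 1 − Σ (k = 0 to r − 1) C(n,k) p^k (1 − p)^(n − k).

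| n | True rate p | Printed | r = 3 (three or more) | r = 4 (more than three) |
|---|---|---|---|---|
| 20 | 20% | 80% | 79.4% | 58.9% |
| 20 | 25% | 91% | 90.9% | 77.5% |
| 10 | 40% | 83% | 83.3% | 61.8% |

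The printed figures reproduce to within one percentage point for three or more events. None reproduces for the written threshold. This discrepancy has nothing to do with radiation attribution and is a separate error.

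**Step 3. Direction of the effect.** Let T be the proportion of patients with any treatment-related Grade 4+ event, and f the share of those patients whose events are all attributed to radiation alone. The counted rate is T × (1 − f). The documents give no value for f, so the values below are assumptions that show the mechanism. With T = 25% and n = 20:

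| Assumed f | Counted rate | P(4 or more counted) | P(3 or more counted) |
|---|---|---|---|
| 0 | 25% | 77.5% | 90.9% |
| 25% | 18.75% | 53.2% | 75.3% |
| 50% | 12.5% | 23.5% | 46.5% |
| 100% | 0 | 0 | 0 |

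The chance of halting falls as f rises and is unchanged if f = 0. The table does not estimate f.

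**The case against.** The strongest reply is that drug-related may simply be loose drafting. The same paragraph names the combination as its target and sends attribution to a section it describes as covering radiation, so the authors may have meant combination toxicity to count. That is a fair reading. A reader might infer a decision to ignore radiation toxicity, and the documents do not support that. What stands is that an investigator following the text would leave radiation-only events out.

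The gap is also narrow. Every patient receives both drugs two weeks before radiation, and the drug causality rating is yes/no, so an event with a plausible drug contribution can count. The criteria in 10.2.2 are reference guidelines that shift likelihood. They do not automatically exclude an event because radiation contributed.

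Radiation risk is managed elsewhere. Eligibility restricts lesions (Sections 1.4.2.5, 4.1 and 4.2). The dose-limiting toxicity definition in Section 6.4 starts from any Grade 3+ toxicity, whether or not drug-related. All serious adverse events are reported (10.3.2), and there is board review (3.3, 13.2.1), weekly review (14) and early termination for safety (13.3). These are real safeguards and limit the weight of the point. However, the dose-limiting toxicity rule covers six patients and leads to a schedule change (6.2), and the others set no numeric trigger.

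A reader might also put the 1-5% re-irradiation mortality into a calculation and report how much the chance of halting is understated. That is not supported. The figure covers deaths only and applies only to re-irradiated patients, whose share here is unknown. Exclusion 4 removes some high-risk lesions, and some such deaths would be rated drug-related and already count.

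**Conclusion.** The point holds as an inconsistency of wording and cross-reference. As written, the only trial-wide numeric halt omits Grade 4+ events attributed to radiation alone, although the rule is stated to protect against toxicity of the combination, and 10.2.2 does not provide the attribution guidance that 3.3 says it does. This rests on the text and on no assumed rate.

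The size cannot be determined. Only the direction is secure: if radiation-only Grade 4+ events occur, the rule is less likely to halt enrolment than one that counts them; if none occur, nothing changes.

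The mismatch between threshold and probabilities is a second error in the same paragraph. At the printed rates the written rule halts with probability 58.9%, 77.5% and 61.8%, against 80%, 91% and 83% as stated. It should not be read as a measure of the radiation gap.

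**What to change.** Reconcile Section 3.3 with its stated aim and with 10.2.2, 10.3 and 11.2.1:

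- **3.3:** state which events count. The wording that matches the stated aim is Grade 4+ toxicity related to any component of the combination, including protocol radiation. If radiation-only events are meant to be left out, say so and give the reason.
- **10.2.2:** add radiation to the attribution guidance, as 3.3 already says it is there.
- **10.3:** record radiation causality for every Grade 4+ event, not only for those reported as serious.
- **11.2.1:** report relationship to drug, radiation or both.
- **Threshold, as a separate correction:** reconcile more than three with three or more, and restate the probabilities for the event finally counted. The printed figures should not be carried forward unchecked.

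The cost is protocol wording and one causality entry for Grade 4+ events not already reported as serious. No patients or visits are added. The downside of the wider count is a higher chance of halting when radiation-only events occur, so the threshold should be re-examined together with the new definition.

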Both durvalumab and tremelimumab have well established toxicity profiles as a single agent and in combination. However, the combination of durvalumab tremelimumab and palliative radiation has not been previously studied, this study will include a formal safety analysis in the first 6 patients accrued. Enrollment will be halted until these first 6 patients complete the first two cycles of treatment (8 weeks), and are evaluable for acute toxicities (toxicities reported within the 1st 8 weeks after treatment initiation). Specifically, if 2 or more DLTs (Refer to Section 6.4) are observed, then, durvalumab dosing will be modified to 1500 mg IV Q6 weeks x 9 doses and tremelimumab 75mg IV Q6 weeks x 3 doses for the remaining 14 patients (fixed dosing for patients > 30kg). If 1 or fewer DLTs are observed, then an additional 14 patients will be enrolled and treated at the initial dose and schedule of durvalumab and tremelimumab. Patients in the run in phase who experience DLTs will undergo dose modifications described in Appendix 1.

Toxicities will be graded based on CTCAE v. 4 and summarized as the number and percentage of patients with each type of toxicity. Responses will be summarized as frequencies and percentages. The Kaplan Meier method will be used to estimate overall survival and progression free survival. Outcomes will be calculated from the date of study entry to the date of the corresponding event.

We will use multivariate statistics to test the hypotheses that pretreatment intratumoral immune cell phenotype and PD-L1 expression predict response to therapy, and that therapy alters systemic immunophenotype.

Sample Size Determination:

There are multiple ongoing studies in various tumor types exploring the activity of durvalumab and tremelimumab. In a published report of the combination in patients with advanced NSCLC treated on a phase Ib study, Grade 3-4 toxicity was observed in 17% of patients. Similarly, in single institution reports of SBRT with the monoclonal antibody, grade 3 or higher toxicity was reported in 6-16% of patients. With a 20 patient accrual goal, toxicity rates can be estimated to within 22% with 95% confidence. Any toxicity with at least 10% prevalence has at least an 87% chance of being observed. This design allows us to reasonably exclude a clinically significant increase in toxicity with the addition of radiation therapy to the durvalumab and tremelimumab combination as defined by the upper bound of the confidence interval.

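### The 83% chance of stopping within the first 10 patients assumes complete follow-up, so it is only an upper limit on the chance of halting enrolment before patient 11

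*Combined protocol and SAP*

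**What the plan says.** Section 3.3 sets the rule: "Enrollment will be halted if more than 3 patients experience a Grade 4 or higher drug related toxicity", counted "during the trial or up to 30 days after the last investigational drug infusion". The only action attached to the rule is halting enrolment.

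The same paragraph gives three supporting figures. Two concern counts: "The likelihood of observing 3 or more Grade 4+ drug-related DLTs is 80% if the true rate is 20" (percent) and "the likelihood is 91% if the true rate is 25" (percent). The third is worded as a property of the rule: "This rule has an 83% chance of stopping in the 1st 10 patients if the true rate is 40" (percent). None states how much follow-up the patients have when the count is taken.

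On the flow of patients, Section 3.1 says "A maximum of 20 patients will be enrolled". The Synopsis and Section 3.3 pause enrolment once, until the first 6 patients have completed 8 weeks. No later pause or staggering is described, and Section 11.2.4 says "No interim analysis is planned for this study". The Synopsis gives a study duration of 48 months but no accrual rate.

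**The concern.** A statement about stopping within the first 10 patients is a statement about time: it says that enough events will have been seen before an eleventh patient is exposed. A binomial tail contains no time. It takes each patient's outcome as final, whereas under this rule an event may appear months after later patients have entered.

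Safety is the primary endpoint, and the Synopsis describes the triplet as not previously studied. Anyone who relies on Section 3.3 to judge how well later patients are protected could take 83% as the protection delivered, when it is the best that could be delivered.

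**Working it through.** **Inputs from the documents.** Maximum of 20 patients (Section 3.1). 13 doses every 4 weeks or, after modification, 9 doses every 6 weeks (Synopsis, Section 6.2). Window to 30 days after the last infusion (Section 3.3). One 8-week hold after patient 6. Rates of 20%, 25% and 40% (Section 3.3).

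**Step 1: reproduce the printed figures.** With complete follow-up, P(X ≥ 3) = 1 − Σ(k=0..2) C(n,k) pᵏ(1−p)ⁿ⁻ᵏ.
- n=20, p=0.20: 1 − (0.0115 + 0.0576 + 0.1369) = 0.794 (printed 80%)
- n=20, p=0.25: 1 − (0.0032 + 0.0211 + 0.0669) = 0.909 (printed 91%)
- n=10, p=0.40: 1 − (0.0060 + 0.0403 + 0.1209) = 0.833 (printed 83%)

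All three reproduce, at a threshold of 3 and with every outcome known. At more than 3 (4 or more), which is the wording of the rule, the same calculation gives 0.589, 0.775 and 0.618. The printed figures do not come from that threshold.

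**Step 2: length of the window.** 12 intervals × 4 weeks = week 48, and 8 intervals × 6 weeks = week 48. Adding 30/7 = 4.3 weeks gives 52.3 weeks. This is a maximum; a patient who stops early leaves the window 30 days after the last infusion.

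**Step 3: what is known when patient 11 arrives.** As an illustration, assume 1 patient per month, evenly spaced (4.33 weeks apart). Patient 6 enters at week 21.7, patient 7 at 29.7 after the hold, patient 10 at 42.7 and patient 11 at 47. At that moment patient 1 has 47 weeks of follow-up and patient 10 has 4.3. None has reached week 52.

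**Step 4: ceilings that need no timing assumption.** Events in patients 1 to 10 can all, at best, be known before patient 11 enters, so the ceiling there is 0.833. For the full trial, patient 20's own event cannot prevent patient 20 from enrolling, so at most 19 patients count. P(X ≥ 3 | n=19) is 0.763 at 20% and 0.889 at 25%.

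**Step 5: size of the further loss.** Accrual and time to event are assumptions. An accrual rate of 0.6 per month is about the slowest that fits: 48 months less 12 of treatment and 3 of follow-up leaves 33, and 20/33 ≈ 0.6. The simulation keeps the 8-week hold and treats each event as known at once. It counts a stop only if the threshold is reached before patient 20 enters (20% and 25% rates) or before patient 11 enters (40% rate).

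| Assumed accrual and event timing | Threshold 3: 20% / 25% / 40% | Threshold 4: 20% / 25% / 40% |
|---|---|---|
| Complete follow-up (basis of the printed figures) | 79.4 / 90.9 / 83.3 | 58.9 / 77.5 / 61.8 |
| 0.6 per month, evenly spaced; events uniform over 8 weeks | 76.1 / 88.7 / 82.6 | 54 / 73 / 61 |
| 1 per month, random arrivals; exponential event times, median 8 weeks | 66 / 81 / 64 | 42 / 61 / 38 |
| 2 per month, random arrivals; events uniform over 52 weeks | 24 / 36 / 11 | 9 / 16 / 2.5 |

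Repeat runs and small modelling choices move the third row by about a point.

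**The case against.** A reader might infer that all three figures are miscalculated stopping probabilities and that the true chance is clearly lower by a known amount. The documents do not support that.

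- The arithmetic is right. The 80% and 91% are worded as likelihoods of observing events, and as such they are correct. Only the 83% is called a chance of stopping.
- The size of the loss cannot be fixed. With patients about 7.2 weeks apart and every event within 8 weeks, almost everything in patients 1 to 10 is known when patient 11 enters, and the 83% barely moves.
- The last row of the table is an extreme. Spreading events evenly to week 52 supposes that patients stay on drug. Tremelimumab ends after 4 doses, radiation is given around week 3, and treatment may end early for progression or toxicity.

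A reader might also infer that safety goes unwatched after patient 6, or that nothing can be done once patient 20 has entered. That is not so either. Section 14 describes weekly review of adverse events, Sections 3.3 and 13.2.1 provide board monitoring, and Section 13.3 allows the study to be terminated for safety. The absence of an interim analysis does not mean that the toxicity count goes unchecked.

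It could be argued that the events meant are short-window DLTs, since the 80% sentence uses that word. Section 6.4, however, limits DLTs to 28 days in the run-in patients, while the rule counts events over the whole trial.

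These points limit the size and reach of the concern. They leave its core standing: the 83% sentence claims timely stopping, and the calculation behind it has no time in it. The other safeguards are real, but the printed probability does not describe them.

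**Conclusion.** The concern holds for the 83% sentence as a matter of interpretation. The figure is the complete-follow-up probability of 3 or more events in 10 patients, and therefore an upper limit on the chance of halting before patient 11 enters. The 80% and 91% stand as worded but should not be read as chances of halting enrolment; those cannot exceed 76% and 89% at a threshold of 3. These ceilings follow from the documents alone.

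Anything beyond them rests on assumed accrual and event timing. At a threshold of 3, the 83% could remain about 83%, fall to about 64%, or fall much further if accrual is fast and events are late. No single corrected value can be given.

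A separate mismatch in the same paragraph has to be settled first, because it changes every figure: the rule says more than 3 and the probabilities use 3 or more. At more than 3, even complete follow-up gives only 59%, 77% and 62%.

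**What to change.** In Section 3.3:

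1. Reconcile the threshold between the rule and its probabilities, and the term DLT with the whole-trial window. Compute every figure at the reconciled threshold.
2. Label the binomial figures as the probability that the count is reached once all 20 (or 10) patients have completed the toxicity window.
3. Delete the sentence on stopping in the first 10 patients, or replace its figure with the probability of halting before patient 11, and add the probability of halting before patient 20. Show both as a range, with the accrual rate, the 8-week hold, the event-time distribution and the delay before an event is counted all stated.

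The cost is a short simulation and a few sentences. The stated stopping probabilities will look less favourable. No extra patients or procedures are needed.
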